[figure not shown]
221 Investigator's Name: _____

222 Clinical Center Name/Number:

PROTOCOL SUMMARY

PARTICIPANT AREA	DESCRIPTION
Title	The International Diabetes Closed Loop (iDCL) trial: Clinical Acceptance of the Artificial Pancreas in Pediatrics- A study of t:slim X2 with Control-IQ Technology
Précis	A randomized controlled trial of at-home closed loop system vs. standard of care (defined as either sensor-augmented pump or any kind of low predictive low blood glucose suspend [PLGS; LGS] if participant is currently using) in youth age 6 to 13 years old.
Investigational Device	t:slim X2 with Control-IQ and Dexcom G6 system
Objectives	The objective of the study is to assess efficacy and safety of a closed loop control (CLC) system (t:slim X2 with Control-IQ Technology) in a randomized controlled trial with partial crossover.
Study Design	First phase a 16-week parallel group randomized clinical trial with 3:1 randomization to intervention with the closed loop system vs. standard of care (SC); followed by a 12-week period where the Standard of Care (SC) group will transition to use CLC and the experimental arm will extend the use of CLC for the same period
Number of Clinical Centers	Up to 4 US clinical centers
Endpoint	The primary outcome for the first phase is time in target range 70-180 mg/dL measured by CGM in CLC group vs. SC group over 16 weeks The primary outcome for the extension phase is improving time in range 70-180 mg/dL by CGM when SC (control group) transitions to t:slim X2 with Control-IQ compared with the same group during the Main Phase.
Population	Key Inclusion Criteria 
 • Type 1 Diabetes • Ages ≥ 6 and ≤ 13 years old Key Exclusion Criteria 
 • Use of any non-insulin glucose-lowering agents except metformin • Actively using any other closed-loop system
Sample Size	First phase: Up to 150 screened participants with the goal of randomizing 100 participants in this 16-week randomized trial. Extension phase will consist of a partial crossover: All randomized participants will participate in an extension phase for another 12 weeks (total 28 weeks). The SC group (control group) will crossover to use Tandem t:slim X2 with Control-IQ for 12 weeks. The experimental arm will continue on the Control-IQ for 12 weeks.

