888 The schedule for remaining follow-up visits and phone contacts is the same for both treatment
889 groups. Study staff will discuss with the participant that periodic contact is required and will make
890 arrangements with the participant for the contacts. If the participant or parent/guardian, cannot be
891 reached, the participant's other contact methods will be utilized, including the emergency contact.

892 **5.4.1 Follow-up Visits**

893 Follow-up visits in clinic will occur at:

- 894 • 2 week (± 3 days)
- 895 • 8 weeks (± 1 week)
- 896 • 16 weeks (+1 week) – end of Main Study Phase

897 **5.4.1.1 Procedures at Follow-up Visits**

898 Procedures performed in both groups at each visit, unless otherwise specified below:

- 899 • Assessment of compliance with study device use by review of any available device data
- 900 • Assessment of adverse events, adverse device effects, and device issues
- 901 • Download of device data (study system or personal pump and study CGM, study BG meter,
902 study ketone meter)

903 **5.4.2 Phone Contacts**

904 In addition to the 1-week phone contact described above for the respective treatment groups, the
905 following phone contacts will be made:

- 906 • 4 weeks (± 3 days)
- 907 • 6 weeks (± 3 days)
- 908 • 10 weeks (± 3 days)
- 909 • 12 weeks (± 3 days)
- 910 • 14 weeks (± 3 days)

911 At each phone contact, the following procedures are performed in both treatment groups:

- 912 • Review of available CGM and/or system data to identify any safety issues associated with
913 insulin pump settings and current diabetes management approach
- 914 • Assessment of adverse events, adverse device effects, and device issues

915 Additional phone contacts may be performed as needed.

916 **5.4.3 Data from Study Devices**

917 All participants will be asked to upload data from the CGM at least once every 4 weeks during the
918 extension phase. The study staff will confirm that the data were received.

919 **5.4.4 16-Week Final First Phase Visit**

920 All participants will return to the clinic for a 16-Week (+7 days) final clinic visit during which the
921 following will occur:

- 922 • HbA1c determination using the DCA Vantage or similar point of care device
- 923 • Collection of a blood sample to send to the central laboratory for HbA1c determination
- 924 • Completion of questionnaires
- 925 • Weight and height measurement will be repeated
- 926 • Assessment of adverse events, adverse device effects, and device issues

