- 927 • Download of device data (study system or personal pump and study CGM, study BG meter,
928 study ketone meter)

929 **5.5 Early Termination Visit (If Applicable)**

930 Participants will be asked to come for an end of study visit in the event of withdrawal or early
931 termination.

932 **5.6 Unscheduled Visits**

933 Participants may have unscheduled visits during the study period if required for additional device
934 training or other unanticipated needs per the study investigator discretion.

935 **5.7 Participant Access to Study Device at Study Closure**

936 Participant will return all investigational study devices and supplies (insulin pump, CGM and
937 related supplies) at study closure. Participant may keep the study ketone meter and study
938 glucometer if these devices are not marked for investigational use only.

939

Chapter 6: Extension Phase Procedures

940 At the conclusion of the 16-week visit, all participants will have the option to use of the Control-
941 IQ closed-loop system.

942 **6.1 Closed Loop Control Participants**

943 Participants who have completed the 16-week Main Study Phase will be provided the option to
944 continue the use the t:slim with Control-IQ System for an additional 12 weeks.

945 The following phone contacts will be made for CLC Group participants in the Extension Phase:

946 • 20 week (± 3 days)
947 • 24 week (± 3 days)

948 At each phone contact, the following procedures are performed:

949 Review of available CGM and/or system data to identify any safety issues associated with insulin
950 pump settings and current diabetes management approach

951 • Assessment of adverse events, adverse device effects, and device issues

952 **6.2 SC Group Participants**

953 Training on pump (section 5.2) use will be provided and therapy optimization will occur as
954 follows:

955 • If needed at the criteria of the physician at each clinical center, optimization may be done at
956 either phone contacts or in clinic visits.
957 • If the study participant contacts the study physician due to concerns about their pump settings
958 due to recurring hypo- or hyperglycemia.

959 Data will be obtained from CGM and/or pump downloads at the visit. Adjustments to pump
960 settings (basal rates, correction factor, insulin-to-carbohydrate ratio, etc.) will be made in response
961 to major trends observed in the CGM data, with flexibility for clinicians to adhere to guidelines

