 1582 for the primary outcome. For the binary CGM outcomes, risk-adjusted percentages by treatment
 1583 group will be calculated from a logistic regression model.

1584 *HbA1c*

1585 Summary statistics ($\text{mean} \pm \text{SD}$) will be reported for the central lab HbA1c at baseline, 16 weeks
 1586 and for differences from pre-randomization by treatment group.

1587 Change in HbA1c from baseline to 16 weeks will be compared between the two treatment arms
1588 using a linear model while adjusting for baseline HbA1c, age, prior CGM and pump use, and
1589 clinical center (random factor).

1590 For extension phase, efficacy of the AP will be compared by using the final 12 weeks of the
1591 control period vs. the 12-week AP extension phase. Each participant will be their own control.

1592 Missing data will be handled using direct likelihood in a regression model including all available
1593 central laboratory HbA1c measurements at baseline and 16-week visits. When available, the
1594 local HbA1c measurement will be included in the regression model as an auxiliary variable.

1595 For the binary HbA1c outcomes listed above, risk-adjusted percentages by treatment group will
1596 be computed from a logistic regression model. The logistic regression will adjust for the same
1597 factors mentioned above for the analysis with HbA1c as a continuous factor (i.e., baseline
1598 HbA1c, age, prior CGM and pump use, and clinical center as a random effect).

1599 **Questionnaires and Other Outcomes**

1600 For questionnaires administered to both randomization groups, comparisons will be made using
1601 similar linear models as described above for the primary outcomes. Separate models will be run
1602 for the total score and each of the subscales listed above.

1603 Similarly, for insulin, weight and BMI metrics comparisons will be made using similar linear
1604 models as described above for the primary HbA1c analysis.

1605 **11.8 Safety Analyses**

1606 All randomized participants will be included in these analyses and all their post-randomization
1607 safety events will be reported.

1608 Safety analyses of the main study (randomized trial phase) will include events occurring on or
1609 after randomization until and including the 16-week visit or Day 126 from randomization,
1610 whichever occurs first. Safety analyses of the extension phase will include subsequent events
1611 until the last visit date or the last event date (whichever is later).

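### The extension-phase primary outcome is a before-after change in at most about 25 SC children, and the concurrent CLC follow-up is not used to check it for period effects

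*Protocol*

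**What the plan says.** The Protocol Summary (Endpoint row) states: "The primary outcome for the extension phase is improving time in range 70-180 mg/dL by CGM when SC (control group) transitions" to the study system, "compared with the same group during the Main Phase". The only analysis text is in Protocol 11.7.2: "For extension phase, efficacy of the AP will be compared by using the final 12 weeks of the", continuing "control period vs. the 12-week AP extension phase. Each participant will be their own control". No model, period term or comparison with the CLC arm is given. The sentence sits under the HbA1c sub-heading, but 12-week windows suit a CGM metric, so I read it as serving the time-in-range outcome. If it does not, that outcome has no stated analysis at all.

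The two places also differ on the comparison period: the whole Main Phase in the Summary, its final 12 weeks (about weeks 5 to 16) in 11.7.2.

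The SAP covers the 16-week randomized trial and contains no extension analysis. SAP section 12 says the randomized trial will be analysed before the extension is complete.

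The CLC arm is followed over the same weeks. The Summary says "The experimental arm will continue on the Control-IQ for 12 weeks"; Protocol 6.1 offers these children the option to "continue the use the t:slim with Control-IQ System for an additional 12 weeks". Section 5.4.3 covers both arms: "All participants will be asked to upload data from the CGM at least once every 4 weeks during the" extension. Table 2 schedules CLC device downloads at weeks 20, 24 and 28.

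**The concern.** Every SC child switches in the same direction at the same study time, week 16. Whatever else moves time in range between weeks 5-16 and weeks 17-28 is added to the effect of starting the device. Ageing and time in study necessarily move with the switch; a calendar effect does so to the extent that it does not average out over entry dates. Section 11.7.2 nevertheless calls the contrast efficacy of the artificial pancreas, and the Summary calls the outcome primary.

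A concurrent group that does not change system is already being observed. If the plan leaves it out now, any later choice to use it would be made with the randomized results known.

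**Working it through.** **1. The plan's own figure.** Protocol 11.3 gives 3:1 allocation, 90% power, a 10-point difference, effective SD 10 and two-sided 0.05. SC size = (1 + 1/3) × [10 × (1.960 + 1.282)/10]² = 14.01, rounded up to 15; with 45 CLC the total is 60, as stated. This sizes the main phase. No size or power is given for the extension outcome.

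**2. Extension numbers.** 100 at 3:1 gives 25 SC and 75 CLC. These are upper bounds, because Protocol 2.1 speaks of those who completed the main study and Chapter 6 makes the extension optional: "At the conclusion of the 16-week visit, all participants will have the option to use of the Control"-IQ system.

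**3. What each contrast estimates.** Let d be the device effect and p a period shift.
- SC change = d + p.
- CLC change = p, if the shift is additive and common to both arms and nothing else changes in CLC.
- SC change minus CLC change = d under that condition.

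Without covariates or missing data, the two estimates differ by exactly the CLC change.

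**4. Precision.** The SD of the within-child change is not given. I assume 6 to 10 points (a range borrowed from the effective SDs in 11.3), equal in both arms.
- Before-after SE = SD/√25.
- Adjusted SE = SD × √(1/25 + 1/75).
- Ratio = √(4/3) = 1.155.

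| Assumed SD | SE, before-after | SE, adjusted | 95% CI half-width, before-after | 95% CI half-width, adjusted |
|---|---|---|---|---|
| 6 | 1.20 | 1.39 | 2.48 | 2.75 |
| 10 | 2.00 | 2.31 | 4.13 | 4.58 |

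At SD 10, power for a 10-point effect is 99.8% before-after and 99.0% adjusted; for a 5-point effect, 67% and 57%. With 20 SC and 60 CLC (an assumed attrition case), power for 10 points is 98.9% and 96.9%.

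**5. Sensitivity to a period shift.** The documents give no shift size, so these are assumed values. If d = 0, the before-after test in 25 children rejects at the following rates (noncentral t):

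| Assumed shift (points) | SD 6 | SD 10 |
|---|---|---|
| 2 | 36% | 16% |
| 3 | 67% | 30% |
| 5 | 98% | 67% |

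A shift common to both arms cancels in the adjusted contrast, which stays at 5%. If the device does work, the same 2 to 5 points appear as bias in the estimate.

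**6. Scheduled contacts** (Protocol Tables 1 to 3).

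| Arm | Weeks 5-16 | Weeks 17-28 |
|---|---|---|
| SC | 6, 8, 10, 12, 14, 16 (six) | 17, 19, 21, 23, 25, 28 (six) |
| CLC | 6, 8, 10, 12, 14, 16 (six) | 20, 24, 28 (three) |

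The number of contacts is constant in SC and halves in CLC. Under Protocol 6.2, SC also receives device training at the switch.

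**The case against.** The strongest reply is that the alternative is also biased, possibly in the device's favour. The schedules bear this out: if fewer contacts lower CLC time in range, subtracting the CLC change inflates the adjusted estimate. SC alone receives new device training, which the CLC arm cannot estimate. Waning in established CLC users would push the adjusted estimate up, and continued learning would push it down. A common additive shift is also untestable between arms that may sit at different levels; the ski-camp home phase showed 71.0 ± 6.6 against 52.8 ± 13.5. All of this stands. It is why the CLC contrast should be supportive and not a replacement.

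It is also fair that the own-control design is openly stated, that Chapter 11 calls itself a framework, and that the randomized main phase already answers the efficacy question on the same outcome. That limits the point to the extension claim, but does not supply a period control or a caveat there.

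Two stronger readings are tempting. A reader might infer that a change in contact frequency confounds the SC comparison; the schedules show six contacts in each period. A reader might also infer that season and school calendar are fully confounded with the switch. Children enter individually, with the run-in skipped or lasting about 2 to 6 weeks, and no enrolment window is stated, so only a net calendar shift can be claimed.

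**Conclusion.** The point holds for the extension phase. Its named primary outcome is a one-direction change in at most about 25 children, and the stated analysis cannot separate the device from ageing, time in study and any net calendar shift. An unadjusted shift enters one-for-one; 2 to 5 points is an assumed range, against the 10-point difference used to size the main phase. The supportive contrast costs about 15% in standard error, assuming equal change SDs of 6 to 10 points and full participation at 25/75.

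A reader might go further and infer that the extension result cannot be attributed to the device at all. The documents do not support that: the concurrent randomized comparison bears on the same device and outcome, and the two estimates may well agree. The main-phase conclusion is unaffected.

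**What to change.** Add one paragraph to Protocol 11.7.2, or to a SAP section for the extension, before the randomized results are known.

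- Keep the within-SC change as the stated outcome, and describe it as a before-after change.
- Pre-specify a supportive mixed model with arm, period (final 12 main-phase weeks against the 12-week extension) and arm-by-period. Report SC change minus CLC change with a 95% CI beside the within-SC change and its 95% CI.
- Attribute the within-SC change to the device only if the two estimates agree, and define agreement in advance (for example, same direction with both intervals excluding zero).
- State the limits: common additive period effects are assumed; scheduled CLC contacts fall from six to three while SC stays at six, and only SC is newly trained, so the adjusted estimate may overstate the device effect; learning or waning in CLC would also bias it.
- Reconcile the comparison period between the Summary and 11.7.2, and place the text under the time-in-range outcome.

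The cost is one model on data already scheduled for collection, with no new visits or participants, and an interval about 11% wider for the supportive estimate (4.58 against 4.13 points at SD 10).

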962 and practices established at each individual practice rather than a fixed set of characteristics for all
963 clinical centers.

964 The following phone contacts will be made for SC Group participants in the Extension Phase:

965 • 17 weeks (± 3 days)
966 • 19 weeks (± 3 days)
967 • 21 weeks (± 3 days)

968 • 25 weeks (± 3 days)

969 At each phone contact, the following procedures are performed:

970 • Review of available CGM and/or system data to identify any safety issues associated with
971 insulin pump settings and current diabetes management approach

972 • Assessment of adverse events, adverse device effects, and device issues

973 Follow-up visits for SC group during the Extension Phase in clinic will occur at:

974 • 23 Weeks (± 1 week)

975 • 28 Weeks (+1 week) – End of Study

976 Procedures Specific to the 28 Week Visit

977 • HbA1c determination using the DCA Vantage or similar point of care device

978 • Collection of a blood sample to send to the central laboratory for HbA1c determination

979 • Completion of questionnaires

980 • Weight measurement will be repeated, in addition to height

981 • Insulin Pump Optimization as described above

982 **6.3 Early Termination Visit (If Applicable)**

983 Participants will be asked to come for an end of study visit in the event of withdrawal or early
984 termination.

985 **6.4 Unscheduled Visits**

986 Participants may have unscheduled visits during the study period if required for additional device
987 training or other unanticipated needs per the study investigator discretion.

988 **6.5 Participant Access to Study Device at Study Closure**

989 Participant will return all investigational study devices and supplies (insulin pump, CGM and
990 related supplies) at study closure. Participant may keep the study ketone meter and study
991 glucometer if these devices are not marked for investigational use only.

992

Chapter 7: Study Devices

993 **7.1 Description of the Investigational Device**

994 **7.1.1 Insulin Pump**

995 The study system will include the Tandem t:slim X2 with Control-IQ technology.

996 **7.1.2 Continuous Glucose Monitoring**

997 The study CGM will include Dexcom G6 transmitter and sensors when using the Tandem t:slim
998 X2 with Control-IQ technology. This may not be an FDA-approved device system at the start of
999 the study, but may become approved during the course of the study. The CGM sensor will be
1000 replaced at least once every 10 days.

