- 1284 ○ The outcome of an ongoing event at the time of death that was not the cause of death, will
1285 be updated and recorded as “resolved” with the date of death recorded as the stop date.

- 1286 • UNKNOWN – An unknown outcome is defined as an inability to access the participant or the
1287 participant's records to determine the outcome (for example, a participant that was lost to
1288 follow-up).

1289 All clinically significant abnormalities of clinical laboratory measurements or adverse events
1290 occurring during the study and continuing at study termination should be followed by the
1291 participant's physician and evaluated with additional tests (if necessary) until diagnosis of the
1292 underlying cause, or resolution. Follow-up information should be recorded on source documents.

1293 If any reported adverse events are present when a participant completes the study, or if a participant
1294 is withdrawn from the study due to an adverse event, the participant will be contacted for re-
1295 evaluation within 2 weeks. If the adverse event has not resolved, additional follow-up will be
1296 performed as appropriate. Every effort should be made by the Investigator or delegate to contact
1297 the participant until the adverse event has resolved or stabilized.

1298 **9.2 Reportable Device Issues**

1299 All UADEs, ADEs, device complaints, and device malfunctions will be reported irrespective of
1300 whether an adverse event occurred, except in the following circumstances.

1301 The following device issues are anticipated and will not be reported on a Device Issue Form but
1302 will be reported as an Adverse Event if the criteria for AE reporting described above are met:

- 1303 • Component disconnections
- 1304 • CGM sensors lasting fewer than the number of days expected per CGM labeling
- 1305 • CGM tape adherence issues
- 1306 • Pump infusion set occlusion not leading to ketosis
- 1307 • Battery lifespan deficiency due to inadequate charging or extensive wireless communication
- 1308 • Intermittent device component disconnections/communication failures not leading to system
1309 replacement
- 1310 • Device issues clearly addressed in the user guide manual that do not require additional
1311 troubleshooting
- 1312 • Skin reactions from CGM sensor placement or pump infusion set placement that do not meet
1313 criteria for AE reporting

1314 **9.3 Pregnancy Reporting**

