1612 Any pre-randomization adverse events will be tabulated separately and will include all
1613 participants even if never randomized.

1614 For the following outcomes, mean \pm SD or summary statistics appropriate to the distribution will
1615 be tabulated by treatment group and formal statistical comparisons (main study phase only) will
1616 be performed if there are enough events (at least 5 events combined between the two treatment
1617 groups):

- 1618 • Number of SH events and SH event rate per 100 person-years
- 1619 • Number of DKA events and DKA event rate per 100 person-years
- 1620 • Any adverse event' rate per 100 person-years

1621 • Number of calendar days with any ketone level ≥ 1.0 mmol/L
1622 • CGM-measured hypoglycemic events (≥ 15 minutes with glucose concentration < 54 mg/dL)
1623 • CGM-measured hyperglycemic events (≥ 15 minutes with glucose concentration > 300
1624 mg/dL)

1625

1626 If enough events, the numbers of SH/DKA events will be compared between the two treatment
1627 arms during the main study phase using a robust Poisson regression. The regression will adjust
1628 for the participant-reported number of events prior to the start of the study and clinical center as
1629 random effect. The amount of follow up will be included as an offset covariate to compare the
1630 rates. Similar analyses will be done for comparing any adverse event and number of calendar
1631 days with ketone events between the two treatment groups, except that clinical center will be the
1632 only covariate to be adjusted in the model.

1633 For CGM-measured hypoglycemia/hyperglycemia events, event rates per week will be compared
1634 using similar linear mixed effects regression models as described above for the primary outcome.

1635

1636 For both the main study and extension phases, the following safety outcomes will be tabulated by
1637 treatment group without a formal statistical comparison:

1638 • Other serious adverse events (SAE)
1639 • BG-measured hypoglycemic events (days with at least one BG record < 54 mg/dL)
1640 • BG-measured hyperglycemic events (days with at least one BG record > 350 mg/dL)
1641 • Worsening of HbA1c from baseline to 16 weeks by $> 0.5\%$
1642 • Investigational device related (intervention group only):
1643 ○ Adverse device effects (ADE)
1644 ○ Serious adverse device events (SADE)
1645 ○ Unanticipated adverse device effects (UADE)

1646

1647 **11.9 Intervention Adherence**

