Précis	A randomized controlled trial of at-home closed loop system vs. standard of care (defined as either sensor-augmented pump or any kind of low predictive low blood glucose suspend [PLGS; LGS] if participant is currently using) in youth age 6 to 13 years old.
Investigational Device	t:slim X2 with Control-IQ and Dexcom G6 system
Objectives	The objective of the study is to assess efficacy and safety of a closed loop control (CLC) system (t:slim X2 with Control-IQ Technology) in a randomized controlled trial.
Study Design	A 16-week parallel group randomized clinical trial with 3:1 randomization to intervention with the closed loop system vs. standard of care (SC).
Number of Clinical Centers	Up to 4 US clinical centers
Endpoint	The primary outcome for the first phase is time in target range 70-180 mg/dL measured by CGM in CLC group vs. SC group over 16 weeks
Population	Key Inclusion Criteria 
Type 1 DiabetesAges \geq 6 and \leq 13 years old Key Exclusion Criteria 
Use of any non-insulin glucose-lowering agents except metforminActively using any other closed-loop system
Sample Size	Up to 150 screened participants with the goal of randomizing 100 participants in this 16-week randomized trial.
Treatment Groups	
Intervention Group: t:slim X2 with Control-IQ Technology and Study CGM.Control Group: Standard of care (SC) (defined as either sensor-augmented pump or any kind of low or predictive low blood glucose suspend [PLGS; LGS] if participant is currently using), and study CGM
Participant Duration	16-20 weeks (depending on duration of run-in phase)
Protocol Overview/Synopsis	After consent is signed, eligibility will be assessed. Eligible participants not currently using an insulin pump and Dexcom G4, G5 or Dexcom G6 CGM with minimum data requirements will initiate a run-in phase of 2 to 4 weeks that will be customized based on whether the participant is already a pump or CGM user. Participants who skip or successfully complete the run-in will be randomly assigned 3:1 to the use of closed-loop control (CLC group) system using Tandem t:slim X2 with Control-IQ Technology vs SC for 16 weeks.

10 The following table provides overview of the schedule of study visits, phone contacts, and key procedures.

11

12 **Table 2. Schedule of Study Visits and Procedures**

	Pre	Pre	0	1w	2w	4w	6w	8w	10w	12w	14w	16w
Visit (V) or Phone (P)	V	V	V	P	V	P	P	V	P	P	P	V

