311 *Boxplots*

312 Boxplots stratified by treatment group will be given for the primary outcome and each of the key
313 secondary endpoints listed in Section 6.2.1 in 4week and 1-week periods over the course of 16 weeks
314 intervention.

315 **7. Safety Analyses**

316 All randomized participants will be included in these analyses and all their post-randomization safety
317 events will be tabulated. Events occurring from the randomization date until and including the 16-week
318 visit date or randomization date + 126 days whichever is earlier will be included.

319 Any pre-randomization adverse events will be tabulated separately and will include participants who
320 were never randomized.

321 For the following outcomes, mean \pm SD or summary statistics appropriate to the distribution will be
322 tabulated by treatment group and formal statistical comparisons will be performed if there are enough
323 events (at least 5 events combined over both treatment groups):

- 324 • Number of SH events and SH event rate per 100 person-years
- 325 • Number of DKA events and DKA event rate per 100 person-years
- 326 • Any adverse event rate per 100 person-years
- 327 • Number of calendar days with any ketone level ≥ 1.0 mmol/L (if ≥ 5 total calendar days
328 combined)
- 329 • CGM-measured hypoglycemic events (≥ 15 minutes with glucose concentration < 54 mg/dL)
- 330 • CGM-measured hyperglycemic events (≥ 15 minutes with glucose concentration > 300 mg/dL)

332 If there are at least 5 SH events combined over both treatment groups, the rates will be compared using a
333 robust Poisson regression. The regression will adjust for the participant-reported number of SH events
334 12 months prior to the start of the study and clinical center as random effect. The amount of follow up
335 will be included as an offset covariate to compare the rates. If one of the treatment groups has zero
336 events then a Poisson model will not converge and Fisher's exact test will be used instead. A similar
337 analysis will be done for DKA if there are at least 5 total DKA events among both treatment groups
338 combined. For any adverse event and number of calendar days with ketone event, similar analyses will
339 be done except that clinical center will be the only covariate to be adjusted in the model.

340 The calculation for the two continuous CGM-measured outcomes will be based on the same inclusion

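### The extension-phase safety window can be lengthened by an event, so any resulting bias in the extension event rates is upward

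*Protocol*

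**What the plan says.** - **Main phase.** Protocol 11.8 includes events on or "after randomization until and including the 16-week visit or Day 126 from randomization", taking the earlier date. SAP Section 7 has the same rule: "visit date or randomization date + 126 days whichever is earlier will be included".
- **Extension phase.** The next sentence of Protocol 11.8 includes subsequent events "until the last visit date or the last event date (whichever is later". There is no latest date, and the text does not say whether the last event is the child's own or the last in the study.
- **SAP scope.** The SAP's study design is "A 16-week parallel group randomized clinical trial with 3:1 randomization to intervention with the closed loop system vs. standard of care (SC". It gives no extension safety window, so the protocol rule stands.
- **Rates.** The outcomes in 11.8 include "Number of SH events and SH event rate per 100 person-years", with matching entries for DKA and any adverse event. Formal comparison is limited to the main phase. Tabulation is not so limited, so I read these rates as also being tabulated for the extension. Follow-up time is mentioned only as the offset in the main-phase Poisson model; extension person-time is not defined.
- **Contacts.** In the extension, CLC children have phone contacts at weeks 20 and 24 and one clinic visit, at week 28 (6.1 and Table 2). SC children have phone contacts at weeks 17, 19, 21 and 25 and clinic visits at weeks 23 and 28 (6.2 and Table 3). Nothing is scheduled after week 28.
- **Withdrawal.** Protocol 10.3 uses a withdrawn participant's data only up to the time of withdrawal.

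**The concern.** An event rate is interpretable when the observation period is set without reference to the outcome. Here a child with no late event is closed at the last visit, while a child with one stays under observation until that event. Time after the last visit therefore enters the analysis only where it produced an event. Two adjacent sentences of 11.8 use opposite rules, so rates from the two phases rest on different footings even if they appear in the same table.

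What is at stake is the description of safety in the extension. Protocol 1.2 gives additional exposure to the system as a purpose of that phase, and it is the SC children's only use of Control-IQ in the trial. The person-time is small, so a few misallocated events would show.

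**Working it through.** The plan states no extension event rate, person-time or bias, so there is no figure to reproduce. The check asks which way the rule can move a rate, and by how much under stated assumptions.

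**Inputs from the documents.** The extension lets CLC children "continue the use the t:slim with Control-IQ System for an additional 12 weeks", so T = 84 days (91 if the week-28 visit uses its +1 week window in 6.2). The goal is 100 randomized at 3:1, about 75 CLC and 25 SC.

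**Assumed, because the documents do not give them.** A constant event rate L of 5, 20 or 100 per 100 person-years, the same before and after the last visit; a post-visit period d of 0, 7, 14 or 28 days in which events may come to notice; a share p of those events recorded; dropout of 5% or 10%.

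**Case A: person-time stops at the last visit.** Ratio of reported to true rate = (T + p·d)/T. With T = 84:

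| d (days) | p = 0.25 | p = 0.5 | p = 1 |
|---|---|---|---|
| 0 | 1.00 | 1.00 | 1.00 |
| 7 | 1.02 | 1.04 | 91/84 = 1.08 |
| 14 | 87.5/84 = 1.04 | 91/84 = 1.08 | 98/84 = 1.17 |
| 28 | 1.08 | 1.17 | 112/84 = 1.33 |

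With T = 91, d = 14 and p = 1 the ratio is 105/91 = 1.15.

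**Case B: person-time runs to the last event where that is later.** With p = 1 the ratio is (T + d)/(T + E), where E = d − (1 − exp(−L·d))/L is the mean person-time added per child. For d = 14:
- 5 per 100 person-years: E = 0.013 days, ratio 98/84.013 = 1.166
- 100 per 100 person-years: E = 0.265 days, ratio 98/84.265 = 1.163

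Extending person-time for the affected children hardly helps, because the children without a late event still add nothing.

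**Second route: early leavers.** A CLC child who leaves before week 28 without a termination visit may have week 16 as the last clinic visit. Without an event, that child would add no extension person-time. If exits are uniform over the 84 days and events before exit are reported, a dropout share q gives approximately (1 − q/2)/(1 − q):
- q = 0.05: 0.975/0.95 = 1.03
- q = 0.10: 0.95/0.90 = 1.06 (simulation 1.04 to 1.05 across the three rates)

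**Event-independent end date.** If events and person-time both stop at T, the expected ratio is T/T = 1.00. Simulated values ran from 0.98 to 1.03, which is Monte Carlo error.

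**The case against.** The sentence in 11.8 says which events are included. It does not define person-time, and it does not say that the last event date is taken per child. Including everything also fits the section's opening commitment to report all post-randomization safety events, and an excess of counted events errs on the side of overstating harm. All of this is fair. It makes the bias conditional, but leaves an open-ended, event-driven end date for tables of rates.

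Four stronger readings are tempting, and the documents do not support them.

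1. *The extension rates are biased upward.* This needs an event recorded after a last visit, or early leavers. With neither, the ratio is 1.00.
2. *Post-visit events are sought selectively.* Protocol 9.1.6 ("If any reported adverse events are present when a participant completes the study, or if a participant" is withdrawn for one) arranges re-contact within 2 weeks to re-evaluate events already known. A new event might be mentioned in such a call, but the section does not set up a search for new events.
3. *Late events all occur off the device.* Protocol 6.5 ("Participant will return all investigational study devices and supplies (insulin pump, CGM and" related items) ties the return to study closure, which fits completers. For a CLC child whose last clinic visit was week 16, an event reported at the week-20 call may have occurred on the system and belongs in the rate. The existing clause keeps it, and any replacement must do the same.
4. *One late event shows the size of the bias.* With 75 × 84/365.25 = 17.25 CLC and 25 × 84/365.25 = 5.75 SC person-years, one event adds 100/17.25 = 5.8 or 100/5.75 = 17.4 per 100 person-years. Any single event does that, wherever it falls. It shows how sparse the denominators are and does not estimate bias.

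**Conclusion.** The point holds in conditional form. Read per child, the extension rule lets the outcome lengthen observation without limit, so any bias it causes in the severe hypoglycemia, DKA and any-adverse-event rates is upward, and those rates are not comparable with the capped main-phase rates. The size is unknown. It is nil with no post-visit event and no dropout, about 1.04 to 1.08 with 25% to 50% capture over 14 days, and about 1.08 to 1.33 with full capture over 7 to 28 days. These figures rest on a constant event rate and on assumed post-visit periods and capture shares.

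Only descriptive extension tables are affected. The primary endpoint, the testing hierarchy, the sample size and the main-phase safety comparisons are not. The change is worth making because it is cheap and the extension person-time is small.

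**What to change.** In Protocol 11.8, replace the extension rule with an end date that does not depend on events, for every participant who enters the extension:

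- Close at the 28-week visit or the early-termination visit. If neither takes place, close at the last completed study contact, counting phone contacts, so that on-device events reported by phone are kept.
- Cap the window at a fixed day, as in the main phase. Day 126 is 112 + 14; the same margin on 28 weeks would be 196 + 14 = Day 210.
- Use the same date for counting events and for person-time, and say so.
- Reconcile the rule with 10.3, so that it is clear how withdrawal closes follow-up.
- List events after the closing date separately, outside the rates. All events are then still reported.

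The cost is a few sentences in 11.8, with no new data collection. The downside is that a few late events move from the rate table to a listing.
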